11.4 Data and Safety Monitoring

A Data and Safety Monitoring Committee will oversee the conduct of the study. The Committee consists of four members from outside of the SWOG, 3 SWOG members, 3 non-voting representatives from the National Cancer Institute (NCI), and the Group Statistician (non-voting). The members of this Committee will receive confidential reports every 6 months from the SWOG Statistical Center, and will meet at the Group's bi-annual meetings as necessary. The Committee will be responsible for decisions regarding possible termination and/or early reporting of the study.

12.0 DISCIPLINE REVIEW

Discipline review is not applicable.

13.0 REGISTRATION GUIDELINES

13.1 Registration Timing

Patients must be registered prior to initiation of treatment (no more than seven calendar days prior to planned start of treatment).

13.2 Investigator/Site Registration

Prior to the recruitment of a patient for this study, investigators must be registered members of a Cooperative Group. Each investigator must have an NCI investigator number and must maintain an "active" investigator registration status through the annual submission of a complete investigator registration packet to CTEP.

a. CTEP Investigator Registration Procedures

Food and Drug Administration (FDA) regulations and National Cancer Institute (NCI) policy require all investigators participating in any NCI-sponsored clinical trial to register and to renew their registration annually.

Registration requires the submission of:

- a completed **Statement of Investigator Form** (FDA Form 1572) with an original signature
- a current Curriculum Vitae (CV)
- a completed and signed **Supplemental Investigator Data Form** (IDF)
- a completed **Financial Disclosure Form** (FDF) with an original signature

Fillable PDF forms and additional information can be found on the CTEP website at <http://ctep.cancer.gov/investigatorResources/investigator_registration.htm>.

For questions, please contact the **CTEP Investigator Registration Help Desk** by email at <[contact]>.

b. CTEP Associate Registration Procedures

The Cancer Therapy Evaluation Program (CTEP) Identity and Access Management (IAM) application is a web-based application intended for use by both Investigators (i.e., all physicians involved in the conduct of NCI-sponsored clinical trials) and Associates (i.e., all staff involved in the conduct of NCI-sponsored clinical trials).

Associates will use the CTEP-IAM application to register (both initial registration and annual re-registration) with CTEP and to obtain a user account.

Investigators will use the CTEP-IAM application to obtain a user account only. (See CTEP Investigator Registration Procedures above for information on registering with CTEP as an Investigator, which must be completed before a CTEP-IAM account can be requested.)

An active CTEP-IAM user account will be needed to access all CTEP and CTSU (Cancer Trials Support Unit) websites and applications, including the CTSU members' website.

Additional information can be found on the CTEP website at <http://ctep.cancer.gov/branches/pmb/associate_registration.htm>. For questions, please contact the **CTEP Associate Registration Help Desk** by email at <[contact]>.

c. CTSU Registration Procedures

Each investigator or group of investigators at a clinical site must obtain IRB approval for this protocol and submit IRB approval and supporting documentation to the CTSU Regulatory Office before they can be approved to enroll patients. Study centers can check the status of their registration packets by querying the Regulatory Support System (RSS) site registration status page of the CTSU members' website by entering credentials at <https://www.ctsu.org>. For sites under the CIRB initiative, IRB data will automatically load to RSS.

Note: Sites participating on the NCI CIRB initiative and accepting CIRB approval for the study are not required to submit separate IRB approval documentation to the CTSU Regulatory Office for initial, continuing or amendment review. This information will be provided to the CTSU Regulatory Office from the CIRB at the time the site's Signatory Institution accepts the CIRB approval. The Signatory site may be contacted by the CTSU Regulatory Office or asked to complete information verifying the participating institutions on the study. Other site registration requirements (i.e., laboratory certifications, protocol-specific training certifications, or modality credentialing) must be submitted to the CTSU Regulatory Office or compliance communicated per protocol instructions.

1. Downloading Site Registration Documents:

Site registration forms may be downloaded from the **S1616** protocol page located on the CTSU members' website. Go to <https://www.ctsu.org> and log in to the members' area using your CTEP-IAM username and password

- Click on the Protocols tab in the upper left of your screen
- Click on the SWOG link to expand, then select **S1616**. Click on the Site Registration Documents link.

2. Requirements for **S1616** Site Registration:

- CTSU IRB Certification (for sites not participating via the NCI CIRB)
- CTSU IRB/Regulatory Approval Transmittal Sheet (for sites not participating via the NCI CIRB)

3. Submitting Regulatory Documents:

Submit completed forms along with a copy of your IRB Approval to the CTSU Regulatory Office, where they will be entered and tracked in the CTSU RSS.

ONLINE: www.ctsu.org (members section) →Regulatory Submission Portal

CTSU Regulatory Office
[name]
[name]
[contact]
[contact]

E-mail: [contact] (for regulatory document submission only)

4. Checking Your Site's Registration Status:

Check the status of your site's registration packets by querying the RSS site registration status page of the members' section of the CTSU website. (Note: Sites will not receive formal notification of regulatory approval from the CTSU Regulatory Office.)

- Go to <https://www.ctsu.org> and log in to the members' area using your CTEP-IAM username and password
- Click on the Regulatory tab at the top of your screen
- Click on the Site Registration tab
- Enter your 5-character CTEP Institution Code and click on Go

13.3 OPEN Registration Requirements

The individual registering the patient must have completed the appropriate SWOG Registration Worksheet. The completed form must be referred to during the registration but should not be submitted as part of the patient data.

Patient enrollment will be facilitated using the Oncology Patient Enrollment Network (OPEN). OPEN is a web-based registration system available on a 24/7 basis. To access OPEN, the site user must have an active CTEP-IAM account (check at < <https://eapps-ctep.nci.nih.gov/iam/index.jsp> >) and a 'Registrar' role on either the LPO or participating organization roster.

OPEN will also ask additional questions that are not present on the SWOG Registration Worksheet. The individual registering the patient must be prepared to provide answers to the following questions:

- a. Institution CTEP ID
- b. Protocol Number
- c. Registration Step
- d. Treating Investigator
- e. Credit Investigator
- f. Patient Initials
- g. Patient's Date of Birth
- h. Patient SSN (SSN is strongly encouraged, but optional. Do not enter invalid numbers.)
- i. Country of Residence
- j. ZIP Code
- k. Gender (select one):
 - Female Gender
 - Male Gender
- l. Ethnicity (select one):
 - Hispanic or Latino
 - Not Hispanic or Latino
 - Unknown
- m. Method of Payment (select one):
 - Private Insurance
 - Medicare
 - Medicare and Private Insurance
 - Medicaid
 - Medicaid and Medicare
 - Military or Veterans Sponsored NOS
 - Military Sponsored (Including Champus & Tricare)
 - Veterans Sponsored
 - Self Pay (No Insurance)

- No Means of Payment (No Insurance)
- Other
- Unknown

- n. Race (select all that apply):
- American Indian or Alaska Native
 - Asian
 - Black or African American
 - Native Hawaiian or other Pacific Islander
 - White
 - Unknown

13.4 Registration Procedures

- a. All site staff will use OPEN to enroll patients to this study. OPEN is integrated with the CTSU Enterprise System for regulatory and roster data and, upon enrollment, initializes the patient in the Rave database. OPEN can be accessed at <https://open.ctsu.org>, from the OPEN tab on the CTSU members' side of the website at <https://www.ctsu.org>, or from the OPEN Patient Registration link on the SWOG CRA Workbench.
- b. Prior to accessing OPEN site staff should verify the following:
- All eligibility criteria have been met within the protocol stated timeframes and the affirmation of eligibility on the Registration Worksheet has been signed by the registering investigator or another investigator designate. Site staff should refer to [Section 5.0](#) to verify eligibility.
 - All patients have signed an appropriate consent form and HIPAA authorization form (if applicable).
- c. The OPEN system will provide the site with a printable confirmation of registration and treatment information. Please print this confirmation for your records.
- d. Further instructional information is provided on the OPEN tab on the CTSU members' side of the website at <https://www.ctsu.org> or at <https://open.ctsu.org>. For any additional questions contact the CTSU Help Desk at [name] or [contact].

13.5 Exceptions to SWOG registration policies will not be permitted.

- a. Patients must meet all eligibility requirements.
- b. Institutions must be identified as approved for registration.
- c. Registrations may not be cancelled.
- d. Late registrations (after initiation of treatment) will not be accepted.

14.0 DATA SUBMISSION SCHEDULE

14.1 Data Submission Requirement

Data must be submitted according to the protocol requirements for **ALL** patients registered, whether or not assigned treatment is administered, including patients deemed to be ineligible. Patients for whom documentation is inadequate to determine eligibility will generally be deemed ineligible.

14.2 Master Forms

Master forms can be found on the protocol abstract page on the SWOG website (www.swog.org) and (with the exception of the sample consent form and the Registration Worksheet) must be submitted on-line via the Web; see [Section 14.3a](#) for details.

14.3 Data Submission Procedures

- a. Data collection for this study will be done exclusively through the Medidata Rave® clinical data management system. Access to the trial in Rave is granted through the iMedidata application to all persons with the appropriate roles assigned in Regulatory Support System (RSS). To access Rave via iMedidata, you must have an active CTEP-IAM account (check at <https://eapps-ctep.nci.nih.gov/iam/index.jsp>) and the appropriate Rave role (Rave CRA, Read-Only, Site Investigator) on either the LPO or participating organization roster at the enrolling site.

Upon initial site registration approval for the study in RSS, all persons with Rave roles assigned on the appropriate roster will be sent a study invitation e-mail from iMedidata. To accept the invitation, site users must log into the Select Login (<https://login.imedidata.com/selectlogin>) using their CTEP-IAM user name and password, and click on the “accept” link in the upper right-corner of the iMedidata page. Please note, site users will not be able to access the study in Rave until all required Medidata and study specific trainings are completed. Trainings will be in the form of electronic learnings (eLearnings), and can be accessed by clicking on the link in the upper right pane of the iMedidata screen.

Users that have not previously activated their iMedidata/Rave account at the time of initial registration approval for the study in RSS will also receive a separate invitation from iMedidata to activate their account. Account activation instructions are located on the CTSU website, Rave tab under the Rave resource materials (Medidata Account Activation and Study Invitation Acceptance). Additional information on iMedidata/Rave is available on the CTSU members’ website under the Rave tab at www.ctsu.org/RAVE/ or by contacting the CTSU help Desk at [name] or by e-mail at [contact].

- b. You may also access Rave® via the SWOG CRA Workbench. Go to the SWOG web site (<http://swog.org>) and logon to the Members Area using your SWOG Roster ID Number and password. After you have logged on, click on *Workbenches*, then *CRA Workbench* to access the home page for the CRA Workbench and follow the link to Rave® provided in the left-hand navigation panel.

To access the CRA Workbench the following must be done (in order):

1. You are entered into the SWOG Roster and issued a SWOG Roster ID Number,

2. You are associated as an investigator or CRA/RN at the institution where the patient is being treated or followed,
3. Your Web User Administrator has added you as a web user and has given you the appropriate system permissions to view data for that institution.

For assistance with points 1 and 2 call the Operations Office at [name]. For point 3, contact your local Web User Administrator (refer to the "Who is my Web User Administrator?" function on the swog.org Members logon page).

For difficulties with the CRA Workbench, please email [contact].

- c. Institutions participating through the Cancer Trials Support Unit (CTSU) please refer to the [CTSU Participation Table](#).

14.4 Data Submission Overview and Timepoints

- a. WITHIN 24 HOURS AFTER BASELINE blood COLLECTION:

Submit Blood within 24 hours of collection at baseline, as outlined in [Section 15.0](#).

- b. WITHIN 7 CALENDAR DAYS AFTER REGISTRATION:

Submit the following:

S1616 Onstudy Form

S1616 Baseline Abnormalities Form

Baseline Tumor Assessment Form (RECIST 1.1)

Pathology Report documenting histologic confirmation of melanoma*

Submit radiology reports from all scans performed to assess disease at baseline.*

*NOTE: Upload reports via the Source Documentation: Baseline form in Rave®.

- c. WITHIN 21 to 35 CALENDAR DAYS AFTER REGISTRATION:

Submit tissue specimens as outlined in [Section 15.0](#).

Note: Blood for PBMCs must be submitted **within 24 hours of collection** at Day 28 (+/-) 7 calendar days.

- d. WITHIN 14 CALENDAR DAYS AFTER EACH CYCLE OF TREATMENT

Submit the following:

S1616 Treatment Form

S1616 Adverse Event Form

e. WITHIN 14 CALENDAR DAYS AFTER EACH DISEASE ASSESSMENT UNTIL PROGRESSION/RELAPSE (SEE STUDY CALENDAR FOR SCHEDULE):

Submit the following:

Follow Up Tumor Assessment Form (RECIST 1.1)

Submit radiology reports from all scans performed to assess disease.*

*NOTE: Upload reports via the Source Documentation: Follow-Up form in Rave@.

f. WITHIN 14 CALENDAR DAYS AFTER DISCONTINUATION OF TREATMENT:

Submit the following:

S1616 Off Treatment Notice

S1616 Treatment Form

S1616 Adverse Event Form

g. WITHIN 14 CALENDAR DAYS AFTER PROGRESSION:

Follow Up Tumor Assessment Form (RECIST 1.1)

Submit radiology reports from all scans performed to assess disease.*

*NOTE: Upload reports via the Source Documentation: Follow-Up form in Rave@.

h. AFTER PROGRESSION, SUBMIT EVERY 6 MONTHS FOR THE FIRST 2 YEARS AND THEN ANNUALLY UNTIL 3 YEARS FROM REGISTRATION:

Submit the following:

Advanced Melanoma Follow Up Form

Late Effects Form (if prior to treatment for progression or relapse or a second primary, and prior to non-protocol treatment, the patient experiences any severe [Grade \geq 3] long term toxicity that has not been previously reported)

i. WITHIN 4 WEEKS AFTER KNOWLEDGE OF DEATH:

Submit the Notice of Death documenting death information.

Also submit:

If the patient was still on protocol treatment, the materials specified in [Section 14.4e](#).

or

Advanced Melanoma Follow-Up Form (if the patient was off protocol treatment)

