		Stevens-Johnson syndrome	
		Toxic epidermal necrolysis	
	Urticaria		
VASCULAR DISORDERS			
	Hypotension		

¹ This table will be updated as the toxicity profile of the agent is revised. Updates will be distributed to all Principal Investigators at the time of revision. The current version can be obtained by contacting [contact]. Your name, the name of the investigator, the protocol and the agent should be included in the e-mail.

² Ipilimumab can result in severe and fatal immune-mediated adverse events probably due to T-cell activation and proliferation. These can include (but are not limited to) autoimmune hemolytic anemia, acquired anti-factor VIII immune response, autoimmune aseptic meningitis, autoimmune hepatitis, autoimmune thyroiditis, hepatic failure, pure red cell aplasia, pancreatitis, ulcerative and hemorrhagic colitis, endocrine disorders (e.g., autoimmune thyroiditis, hyperthyroidism, hypothyroidism, autoimmune hypophysitis/hypopituitarism, and adrenal insufficiency), ocular manifestations (e.g., uveitis, iritis, conjunctivitis, blepharitis, and episcleritis), sarcoid granuloma, myasthenia gravis, polymyositis, and Guillain-Barre syndrome. The majority of these reactions manifested early during treatment; however, a minority occurred weeks to months after discontinuation of ipilimumab especially with the initiation of additional treatments.

³ Late bowel perforations have been noted in patients receiving MDX-010 (ipilimumab) in association with subsequent IL-2 therapy.

⁴ Complications including hyperacute graft-versus-host disease (GVHD), may occur in patients receiving allo stem cell transplant (SCT) after

CLOSED FILE

receiving Ipilimumab (MDX-010). These complications may occur despite intervening therapy between receiving Ipilimumab (MDX-010) and allo-SCT.

- ⁵ In rare cases diplopia (double vision) has occurred as a result of muscle weakness (Myasthenia gravis).
- ⁶ Gastrointestinal hemorrhage includes Anal hemorrhage, Cecal hemorrhage, Colonic hemorrhage, Duodenal hemorrhage, Esophageal hemorrhage, Esophageal varices hemorrhage, Gastric hemorrhage, Hemorrhoidal hemorrhage, Ileal hemorrhage, Intra-abdominal hemorrhage, Jejunal hemorrhage, Lower gastrointestinal hemorrhage, Oral hemorrhage, Pancreatic hemorrhage, Rectal hemorrhage, Retroperitoneal hemorrhage, and Upper gastrointestinal hemorrhage under the GASTROINTESTINAL DISORDERS SOC.
- ⁷ Infection includes all 75 sites of infection under the INFECTIONS AND INFESTATIONS SOC.

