11.3 Secondary Objectives

An important hypothesis underlying the rationale for the combination therapy is that initial progression on PD-1 blockade alone results from poor T cell recruitment. Consequently, our first secondary endpoint will evaluate this by comparing the quantitative CD8+ expression levels between patients who eventually respond and patients who do not respond using a two-sample t-test and control the type I error at the two-sided 0.05 level. Assuming that the trial accrues to completion, 90% compliance in tissue and biopsy

submission, there will be 56 patients to evaluate this hypothesis. If it is further assumed that 25% of these patients respond, then we anticipate 80% power to detect a mean difference in CD8+ expression of 0.875 standard deviations. Evaluation of this hypothesis motivates the unbalanced randomization.

For the additional secondary objectives, the study will estimate the response rate (confirmed and unconfirmed, complete and partial responses) in each arm and construct 95% binomial confidence intervals. All randomized patients will be included in the analysis of response. Patients who cannot have their exact response determined due to inadequate disease assessments will be counted in the denominator as non-responders.

We will also construct Kaplan-Meier plots and estimate the median Overall Survival (OS) and construct 95% Brookmeyer-Crowley Confidence intervals. We will be able to estimate the ORR or the OS rates at a particular time point (e.g. 13 weeks) to within 12.3% (95% confidence interval (CI)) and 21.4% in the combination therapy and ipilimumab alone arms, respectively. Waterfall plots will be constructed to represent each patient's best change in tumor burden.

Toxicity will be assessed in each arm separately. Any toxicity with at least 5% chance of occurring has 93.7% and 60.3% chance of being observed at least once in the combination therapy and ipilimumab alone arms, respectively. We will be able to estimate the rate of occurrence of any particular toxicity to within 12.3% (95% CI) and 21.4% in the combination therapy and ipilimumab alone arms, respectively.

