requirement window has been extended to **90** calendar days rather than the normal 30 day requirement.] If there is any question about the reportability of an adverse event or if on-line CTEP-AERS cannot be used, please telephone or email the SAE Specialist at the Operations Office, [name] or [contact], before preparing the report.

CLOSED EFFECTIVE 07/15/2020

**Table 16.1
Late Phase 2 and Phase 3 Studies: Expedited Reporting Requirements for Adverse Events that Occur on Studies under a CTEP IND within 90 Calendar Days of the Last Administration of the Investigational Agent/Intervention¹ Ipilimumab and Nivolumab (Arm 1 and Arm 2)**

FDA REPORTING REQUIREMENTS FOR SERIOUS ADVERSE EVENTS (21 CFR Part 312) NOTE: Investigators MUST immediately report to the sponsor (NCI) ANY Serious Adverse Events, whether or not they are considered related to the investigational agent(s)/intervention (21 CFR 312.64)
 
An adverse event is considered serious if it results in ANY of the following outcomes:
 
 1) Death 2) A life-threatening adverse event 3) An adverse event that results in inpatient hospitalization or prolongation of existing hospitalization for ≥ 24 hours 4) A persistent or significant incapacity or substantial disruption of the ability to conduct normal life functions 5) A congenital anomaly/birth defect. 6) Important Medical Events (IME) that may not result in death, be life threatening, or require hospitalization may be considered serious when, based upon medical judgment, they may jeopardize the patient or subject and may require medical or surgical intervention to prevent one of the outcomes listed in this definition. (FDA, 21 CFR 312.32; ICH E2A and ICH E6). 				

ALL SERIOUS adverse events that meet the above criteria MUST be immediately reported to the NCI via CTEP-AERS within the timeframes detailed in the table below.
				
Hospitalization	Grade 1 Timeframes	Grade 2 Timeframes	Grade 3 Timeframes	Grade 4 & 5 Timeframes
Resulting in Hospitalization ≥ 24 hrs	10 Calendar Days			24-Hour 5 Calendar Days
Not resulting in Hospitalization ≥ 24 hrs	Not required	10 Calendar Days		

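### Section 14.4 lists no routine toxicity form for patients who are off treatment and progression-free, so late-toxicity capture depends on progression and differs by arm

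*Combined protocol and SAP*

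**What the plan says.** Section 16.1a sends routine adverse event reporting to Section 14.0, so the form schedule in 14.4 governs what is recorded.

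- **On treatment (14.4d).** The Adverse Event Form is due "WITHIN 14 CALENDAR DAYS AFTER EACH CYCLE OF TREATMENT".
- **End of treatment (14.4f).** One further Adverse Event Form is due "WITHIN 14 CALENDAR DAYS AFTER DISCONTINUATION OF TREATMENT".
- **Off treatment, before progression (14.4e).** Only the follow-up tumour assessment form and radiology reports are listed.
- **After progression (14.4h).** The Late Effects Form appears here alone, under "AFTER PROGRESSION, SUBMIT EVERY 6 MONTHS FOR THE FIRST 2 YEARS AND THEN ANNUALLY UNTIL 3 YEARS FROM REGISTRATION". It covers Grade 3 or higher long-term toxicity not already reported, and only if it arises "prior to treatment for progression or relapse or a second primary, and prior to non-protocol treatment".

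The study calendar (9.1 and 9.3, footnote P) continues toxicity notation in both follow-up columns, every 3 weeks in Arm 1 and every 4 weeks in Arm 2, but only until adverse events have resolved. Footnote N continues the history and physical exam every 12 weeks until progression.

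On late events, footnote 2 to the ipilimumab adverse event list in Section 3.1 says that most immune reactions came early, and that "a minority occurred weeks to months after discontinuation of ipilimumab especially with the initiation of additional treatments". Section 16.1e notes that the post-dosing expedited reporting "requirement window has been extended to 90 calendar days rather than the normal 30 day requirement".

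Toxicity by arm is secondary objective 1.2d. Section 11.3 says of it: "We will be able to estimate the rate of occurrence of any particular toxicity to within 12.3% (95% CI) and 21.4" percent, for the combination and ipilimumab-alone arms respectively.

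**The concern.** The protocol expects some immune toxicity to appear after dosing stops, and it lengthened the expedited window for that reason or one like it. The routine forms did not follow. Once the off-treatment Adverse Event Form is in, whether a new toxicity has a routine form to go on depends on whether the patient has progressed.

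Two things are at stake. First, the by-arm toxicity rates in 11.3 may omit, or receive late, some severe events in patients whose disease is controlled. Second, the arms are exposed to the gap differently. Arm 1 stops at four cycles by design. Arm 2 continues nivolumab until a Section 7.5 criterion is met, with a form every 28-day cycle. A side-by-side reading of the two toxicity profiles would then compare unequal periods of recording.

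**Working it through.** **1. The plan's own precision figures.** With the half-width 1.96 × 0.5/√n, n = 63 gives 0.123 and n = 21 gives 0.214. These match the stated 12.3% and 21.4%, so they treat every patient as fully observed for toxicity. One unrecorded event moves a rate by 1/21 = 4.8 percentage points in Arm 1 and 1/63 = 1.6 points in Arm 2.

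**2. When routine forms end in Arm 1 (7.2, 14.4).** Without dose delays the fourth dose falls on Day 1 + 3 × 21 = 64. Cycle 4 ends on Day 84, and the last Adverse Event Form is due by Day 84 + 14 = 98. That is 34 days after the last dose, against a 90-day expedited window. The reporting period printed on the forms is not in the documents, so due dates are only a guide to the period covered.

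**3. How many Arm 1 patients enter the gap.** Section 11.2 assumes exponential PFS with a 3-month median in Arm 1, so S(t) = 0.5^(t/3), with 30.4375 days to a month.

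| Time point | Months | S(t) | Of 21 |
|---|---|---|---|
| Week 12 (Day 84) | 2.76 | 0.529 | 11.1 |
| 90 days after dose four (Day 154) | 5.06 | 0.311 | 6.5 |
| 12 months | 12 | 0.0625 | 1.3 |

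PFS runs from registration, which may precede treatment by up to 7 days (13.1). Adding 7 days changes the first two rows to 0.501 (10.5 of 21) and 0.295 (6.2 of 21).

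**4. Delay or loss.** Under an exponential with a 3-month median, a patient who is progression-free at any time has a median of 3 further months to a PFS event. The 14.4h submissions are then six-monthly. For most Arm 1 patients an unreported Grade 3 event is therefore delayed. It is absent only if the patient does not progress within the 3 years of follow-up (7.7) or dies first without progression, when 14.4i does not list the Late Effects Form.

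**5. Arm 2.** Progression-free patients normally remain on treatment. The gap reaches those who stop for toxicity, delay or withdrawal (7.5d to f), and the documents give no rate for this.

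**6. What expedited reporting leaves out.** Table 16.1, footnote 1, still requires reports more than 30 days after the last dose for serious, at least possibly related events: Grades 3 to 5, and Grade 2 with hospitalization. The SPEER exceptions apply to it. The ipilimumab SPEER lists colitis, diarrhea and maculo-papular rash at Grade 3, reportable only above that grade, and 16.1f.2 adds colitis and dermatitis only above Grade 3. A new Grade 3 colitis or diarrhea in a progression-free Arm 1 patient off treatment thus has neither an expedited report nor a routine form until progression. Rash is the same if the ipilimumab list alone governs Arm 1. If the instruction to use the lower grade across the two drugs' lists is applied there too, nivolumab's Grade 2 entry makes a Grade 3 rash reportable.

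**7. The calendar.** Footnote P follows events until they resolve. It does not start a search for new ones, and 14.4 has no form matching it off treatment.

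**The case against.** The strongest case on the other side is that little is actually lost.

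- **Most events are early.** Section 3.1 says so, and 8.7 puts common onset at 3 to 10 weeks from first dose, inside the per-cycle forms. This stands, and it is why the number affected is probably small.
- **Serious late events are still reported.** CTEP-AERS reporting depends on neither progression nor next therapy, and pneumonitis, hypophysitis, adrenal insufficiency and myocarditis have no SPEER exemption for either drug. This also stands. However, such reports are graded under CTCAE 5.0 and routine toxicity under 4.0 (8.1), and 11.3 does not say whether the two sources are combined.
- **The Late Effects Form can look back.** It accepts earlier unreported Grade 3 or higher events once the patient progresses. Correct: for those events the usual result is delay.
- **No between-arm toxicity test is planned.** Section 11.3 assesses each arm separately and does not name its data source. So unequal capture affects a descriptive comparison, not a test.
- **The next-therapy cut-off is a defensible attribution rule.** Agreed; it should stay.

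A reader might go further and infer that late toxicity is never recorded, that both arms are affected alike, or that the protocol calls the period after new therapy the riskiest. The documents do not support these. The first ignores CTEP-AERS and the look-back at progression. It also cannot be verified, because the content of the Advanced Melanoma Follow Up Form is not given. The second ignores continued nivolumab in Arm 2. The third misreads Section 3.1, which singles out new treatment only within the late minority.

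**Conclusion.** The point holds in limited form. As written, 14.4 gives no routine form for new toxicity in a patient who is off protocol treatment and progression-free. The calendar does not fill the gap, and expedited reporting fills it only in part.

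In Arm 1 about 11 of 21 patients would enter the gap at Week 12, and 6 to 7 of 21 would still be in it 90 days after the fourth dose. These counts assume the 11.2 exponential model, no dose delays and 21 eligible patients. In Arm 2 the size cannot be stated.

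These are patients exposed to the gap, not missing events. The documents give no late-event rate, and an assumed rate applied to all 63 Arm 2 patients would be misleading because most progression-free patients there are still submitting forms. The effect on any single rate is likely to be small beside its sampling error: one Arm 1 event is 4.8 points against a half-width of 21.4. It is nevertheless a difference in recording between arms that is easily removed.

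**What to change.** Change 14.4 so that the Late Effects Form is due from the end of protocol treatment, before as well as after progression. Before progression, submit it with the existing 12-weekly history and physical exam (footnote N in 9.1 and 9.3), and add it to the list in 14.4e. State in 11.3 that the by-arm toxicity rates include these forms. Keep the existing cut-off at treatment for progression or non-protocol treatment.

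The cost is wording in 14.4e, 14.4h and 11.3 and slightly more site data entry, with no new visit or test. The form's Grade 3 threshold stays, so new lower-grade late events would still go unrecorded; that limit should be acknowledged when toxicity is reported.
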